Protocol for Roquette: glycaemic response, insulinaemic response, GLP-1 and GIP study

Oxford Brookes Centre for Nutrition and Health (OxBCNH)

Department of Sport, Health Sciences & Social Work

Oxford Brookes University

[name]

[name]

[name]

[contact]

Email: [contact]

<http://www.brookes.ac.uk/oxbcnh>

Aim

The aims of this study are to examine:

- Phase I – the glycaemic response (GR) and insulinaemic response (IR) to:
 - 50 g available carbohydrate
 - 50 g available carbohydrate + protein (dose 1)
 - 50 g available carbohydrate + protein (dose 2)
- Phase II – the GLP-1 and GIP response to:
 - 50 g available carbohydrate
 - 50 g available carbohydrate + protein (dose 1)
 - 50 g available carbohydrate + protein (dose 2)

Study design

A single-blind, randomised, repeat measure, crossover design trial will be used to study the response following consumption of three meals: one reference meal (50 g available carbohydrate) and two test meals (50 g available carbohydrate with protein dose 1 and 50 g available carbohydrate with protein dose 2). The study will be conducted in two phases:

- Phase I: glycaemic response (GR), insulinaemic response (IR)
- Phase II: GLP-1 response and GIP response

Phase II will be dependent on the outcomes from Phase I.

Participants will act as their own controls. Participants will be randomly assigned to test the products using a pseudo-random number generator. The trial will be conducted by the Oxford Brookes Centre for Nutrition and Health (OxBCNH). Ethical approval for the trial will be obtained from the University Research Ethics Committee (UREC) at Oxford Brookes University. Participants will be given full details of the study protocol and the opportunity to ask questions. All participants will give written informed consent prior to participation.

Participants

A sample size of 30 participants will be recruited. Healthy male and female adult participants (aged 18-60 years) will be recruited for the study. Participants will be excluded from the study if they meet any of the following criteria:

- Aged < 18 or > 60 years

- Pregnant or lactating
- Body mass index (BMI) $> 30\text{kg}/\text{m}^2$
- Fasting blood glucose value $> 6.1 \text{ mmol/l}$
- Any known food allergy or intolerance
- Medical condition(s) or medication(s) known to affect glucose regulation or appetite and/or which influence digestion and absorption of nutrients
- Known history of diabetes mellitus or the use of antihyperglycaemic drugs or insulin to treat diabetes and related conditions
- Major medical or surgical event requiring hospitalization within the preceding 3 months
- Use of steroids, protease inhibitors or antipsychotics (all of which have major effects on glucose metabolism and body fat distribution)

In addition, participants will be excluded if they are unable to comply with experimental procedures or do not follow GR and IR testing safety guidelines.

Products

Three meals will be administered:

- 50 g available carbohydrate
- 50 g available carbohydrate + protein (dose 1)
- 50 g available carbohydrate + protein (dose 2)

Protocol

The study will be conducted by Good Clinical Practise (GCP) certified researchers at OxBCNH. The protocol used by OxBCNH is based on ISO standards for the determination of the glycaemic index (GI).¹

On the day prior to a test, participants will be asked to restrict their intake of alcohol and caffeine-containing drinks and to restrict their participation in intense physical activity (for example, long periods at the gym, excessive swimming, running and aerobics). Participants will also be told not to eat or drink after 9.00 pm the night before a test, although water will be allowed in moderation.

The reference meal and two test meals will be administered to participants in a randomised, repeated measures design. In each participant, the meals will be tested in random order on separate days, with a one-week gap between measurements. Participants will be studied in the morning, before 10 am after a 12-hour overnight fast. Participants will consume the products at a comfortable pace, within 15 minutes and will remain sedentary during each session and will not consume any additional food or fluid.

Anthropometric measurements

All anthropometric measures will be taken, using standard methods, in the morning, after an overnight fast (12 hours):

- Height and weight
- BMI will be calculated using the standard formula: weight (kg)/height (m)²
- Waist and hip circumference

¹ Food Products – Determination of the glycaemic index (GI) and recommendation for food classification. ISO 26642: 2010(E)

- Body composition using a body composition analyser (Tanita BC-418 MA; Tanita UK Ltd)

Phase I

Glycaemic response (GR)

The glycaemic response method used by OxBCNH at Oxford Brookes University is carried out in accordance with the ISO 26642:2010 guidelines.¹

Blood samples will be taken at -5 min and 0 min before consumption of the reference product/test product and the baseline value taken as a mean of these two values. The product will be consumed immediately after this and within 15 min. Further blood samples will be taken at 15, 30, 45, 60, 90, 120, 150 and 180 min after starting to drink. The time between participants finishing drinking and the first postprandial blood sample will be recorded.

Blood will be obtained by finger-prick using the Unistik®3 single-use lancing device (Owen Mumford). Capillary blood sampling is preferred for reliable GR testing. Prior to a finger-prick, participants are encouraged to warm their hand to increase blood flow. Fingers are not squeezed to extract blood from the fingertip as this may dilute with plasma. Blood glucose will be measured using the HemoCue Glucose 201+ analyser (HemoCue® Ltd), which is calibrated daily using control solution from the manufacturer.

The incremental area under the blood glucose response curve (iAUC) will be calculated geometrically by applying the trapezoid rule, ignoring the area beneath the baseline.

Insulinaemic response (IR)

Blood samples in the fasting state will be obtained five minutes apart (-5 and 0 min) for measuring baseline insulin levels. Following the consumption of the reference product/test products, further blood samples will be collected at 15, 30, 45, 60, 90, 120, 150 and 180 min after starting to drink.

At each test time point, 300 µL of capillary blood (from finger pricks) will be obtained. Finger pricks will be made using the Unistik 3 single-use lancing device (Owen Mumford, Woodstock, UK) and blood will be collected into chilled Microvette® capillary blood collection tubes treated with di Pottassium EDTA (CB 300 K2E; Sarstedt Ltd, Leicester, UK). The Microvette® tubes will then be centrifuged and 200 µL of the supernatant plasma obtained. Insulin concentrations in the plasma samples will be determined by electrochemiluminescence immunoassay using an automated analyzer (Cobas® E411; Roche diagnostics, Burgess Hill, UK). The Cobas® system is a reliable method of plasma insulin determination². The unit of measurement is µU/ml.

² Siannidou T, Margeli A, Kappis A, Papassotiriou I & Mandyla H. Circulating visfatin levels in healthy preterm infants are independently associated with high-density lipoprotein cholesterol levels and dietary long-chain polyunsaturated fatty acids. *Metabolism* 2010;60(3):389-93

Phase II

GLP-1 and GIP

During Phase I of the study, a cannula will be fitted and baseline measurements (0 min) will be taken before participants are provided with the test meals. Blood samples will then be collected at 30, 60, 90, 120 and 180 min after the start of consumption.

Blood will be taken from the antecubital vein via cannulation and will be centrifuged to obtain plasma samples which will be stored at -80°C until analysis. Depending on the outcome of Phase I, samples will be subsequently analysed to determine the concentrations of GLP-1 and GIP.

Statistical analysis

Data will be analysed using the IBM Statistical Package for the Social Sciences (SPSS, version 24). Data will be presented as mean, standard deviation (SD) and standard error of the mean (SEM) values. The blood glucose, plasma insulin, GLP-1 and GIP iAUC (at 60, 90, 120 and 180 min) will be calculated geometrically by applying the trapezoid rule, according to the ISO standards. Prior to statistical analysis, the normality of the data will be tested using the Shapiro-Wilks statistic. Parametric or non-parametric tests will be used as appropriate to compare the following between the products:

- *Phase I*
 - blood glucose/insulin concentrations
 - peak blood glucose/insulin value and time of the blood glucose/insulin peak
 - glucose/insulin iAUC (at 60, 90, 120 and 180 min)
- *Phase II*
 - GLP-1 and GIP concentrations
 - GLP-1 and GIP iAUC (at 60, 90, 120 and 180 min)

Statistical significance will be set at $P < 0.05$.

Outcomes

- The primary outcome will be the GR and IR, as measured by the incremental area under the curve, blood glucose/insulin concentrations, peak and the time at which peaks occur
- The secondary outcome will be the GLP-1 and GIP incremental area under the curve and concentrations

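### The plan specifies neither balanced meal orders nor a visit term in the analysis; adding both is cheap protection against visit-to-visit drift, with a gain that is probably small

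*Combined protocol and SAP*

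**What the plan says.** The design is a three-meal crossover in which every participant takes the reference meal and both test meals. Four places bear on order and visit:

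- *Study design*: "Participants will be randomly assigned to test the products using a pseudo-random number generator".
- *Protocol*: "The reference meal and two test meals will be administered to participants in a randomised, repeated measures design", and "In each participant, the meals will be tested in random order on separate days, with a one-week gap between measurements".
- *Participants*: "A sample size of 30 participants will be recruited". No power, effect size, within-person SD or dropout allowance accompanies the figure.
- *Statistical analysis*: "Parametric or non-parametric tests will be used as appropriate to compare the following between the products". A Shapiro-Wilk check precedes the choice of test.

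No section mentions blocks, a Latin square, a number of participants per order, or a visit, period or sequence factor.

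**The concern.** Three meals give 3! = 6 possible orders. When each person is measured on three separate days, responses may shift between visits for reasons unrelated to the meal, such as familiarity with the procedure, a change in habits, or laboratory or analyser drift. A crossover normally handles this in two ways: each meal appears equally often at each visit, and visit is a factor in the model. The plan commits to neither.

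What is at stake is precision. If orders are drawn independently and visit is left out, the visit effect becomes extra noise in every meal contrast and widens its confidence interval. The visit term can be added at any time before analysis, but the order list has to be settled before the first meal is given.

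**Working it through.** **Inputs from the documents.** 30 participants, 3 meals, 3 visits each, significance level 0.05.

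**Assumptions.** The documents do not give these: two-sided test; true difference of 0.75 within-person SD between one test meal and the reference; no carryover; visit effects as listed below, in within-person SD. *Drift d* is a linear change of d per visit. *Shift s* means that the first visit differs from the other two by s. The comparator is a three-meal repeated-measures ANOVA without visit, with each participant's order drawn independently. The plan names no test, so this comparator is also an assumption.

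**Plan's own figure.** The sample size of 30 cannot be reproduced, because no power, effect or SD is given.

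**Step 1: balance by chance.** With independent draws, the probability of exactly 5 participants per order is 30!/(5!^6 × 6^30) = 0.0004. In 400,000 draws the median smallest and largest order counts were 2 and 8. The difference between two meals in mean visit number has SD √(2/30) = 0.26 visits. These figures show that balance will not arise unless it is planned. They do not measure harm, since exact balance is not needed for validity.

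**Step 2: cost of the visit term.** Error degrees of freedom are 90 − 30 − 2 = 58 without visit and 90 − 30 − 4 = 56 with it. With balanced orders the variance of a meal contrast is 2/30 either way, so the noncentrality is 0.75/√(2/30) = 2.905. Power is 0.815 on 58 df and 0.815 on 56 df (0.8150 and 0.8145).

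**Step 3: loss if visit is ignored and orders are independent.** Error variance is multiplied by 1 + (sum of squared centred visit effects)/2. For drift d the centred effects are −d, 0, d, which gives 1 + d². For shift s they are 2s/3, −s/3, −s/3 (up to sign), which gives 1 + s²/3. Power on 58 df uses noncentrality 0.75/√(2 × factor/30). The loss is measured from 0.815.

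| Assumed visit effect | Variance factor | Power | Loss (points) | 30 participants worth |
|---|---|---|---|---|
| none | 1.000 | 0.815 | 0 | 30 |
| drift 0.1 | 1.010 | 0.811 | 0.4 | 29.7 |
| shift 0.25 | 1.021 | 0.807 | 0.8 | 29.4 |
| drift 0.2 | 1.040 | 0.800 | 1.5 | 28.8 |
| shift 0.5 | 1.083 | 0.784 | 3.1 | 27.7 |
| drift 0.3 | 1.090 | 0.781 | 3.4 | 27.5 |
| drift 0.4 | 1.160 | 0.756 | 5.9 | 25.9 |
| drift 0.5 | 1.250 | 0.724 | 9.1 | 24.0 |
| shift 1 | 1.333 | 0.696 | 11.9 | 22.5 |

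Simulation (20,000 trials per setting) agrees. Balanced orders plus a visit term give 0.81 to 0.82 in every row. Mean 95% CI width, in within-person SD, is 1.03 with both measures throughout. With neither it is 1.05 at drift 0.2 and 1.15 at drift 0.5.

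**Step 4: each half alone.**

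- *Visit term, orders unbalanced.* Power is about 0.80 throughout. With no visit effect this costs 1 to 2 points (0.813 to 0.798). It breaks even at drift 0.2 (0.802 without the term, 0.801 with it) and gains beyond that, recovering most of the loss at drift 0.5 or shift 1. The break-even follows from the standard errors in a separate run of 8,000 trials: (0.2618/0.2569)² = 1.04, the same factor as drift 0.2 in the table.
- *Balance, no visit term.* The contrast is free of visit effects, but the error mean square still contains them. Its expectation rises by (58 + 60d²)/58, which is 73/58 = 1.26 at d = 0.5. The test becomes conservative: type I error is 0.046 at drift 0.2, 0.042 at 0.3 and 0.030 at 0.5, and little power is recovered.

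**Step 5: dropout.** With 3 or 6 of 30 participants removed at random, power without / with both measures was 0.77 / 0.77 and 0.72 / 0.72 with no visit effect, and 0.75 / 0.77 and 0.70 / 0.72 at drift 0.2. Single missed visits were not simulated.

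**The case against.** The strongest reply is that little is at stake. A pseudo-random number generator can produce a blocked list, and the analysis section names no model, so neither omission is a decision against balance or a visit term. The documents show no sign of drift. The conditions are standardised: visits are a week apart, "Participants will be studied in the morning, before 10 am after a 12-hour overnight fast", and the glucose analyser is "calibrated daily using control solution from the manufacturer". All of this stands. It is why the finding is that the measures are unspecified, and why only the upper rows of the table should guide its weight.

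Four stronger readings are tempting, and none is supported:

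- *The meal comparison is biased or the false-positive rate inflated.* Over randomisations the contrasts are unbiased, and simulated type I error with independent draws is 0.048 to 0.053. An uneven list can tilt one realised contrast, but the loss on average is one of precision.
- *The trial will lose around 10 power points.* That needs drift of 0.5 SD per visit or a first-visit shift of 1 SD. Nothing in the documents points to either.
- *A visit term is only worth having with balanced orders.* Step 4 shows the opposite once drift exceeds about 0.2.
- *Re-drawing the order list would give a valid non-parametric p-value for each pair of meals.* It tests only the hypothesis that all three meals are alike. In simulations with log-normal errors, where two meals were equal and the third differed by a multiplicative factor, the pairwise type I error reached roughly 8% to 11%.

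Dropout is also a fair objection, since "participants will be excluded if they are unable to comply with experimental procedures" and the exact 5 per order may not survive. The visit term still adjusts, and under the dropout simulated the two measures together were no worse than doing neither.

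**Conclusion.** The concern holds as a modest design improvement, for consideration rather than as a required correction. Balance of the six orders and a visit term are both unspecified, 30 = 6 × 5 makes balance possible, and together they cost nothing measurable when there is no visit effect. The likely benefit is 0 to 2 power points, given the standardised conditions and drift of at most 0.2 within-person SD per visit. It grows only under larger assumed drift. Most of the protection comes from the visit term; balance adds about 1 to 2 points.

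The sizes rest on the assumed 0.75 SD difference, the assumed visit effects, normal errors and an ANOVA comparator that the plan does not name. Confidence is medium for that reason. If the list is already balanced, the visit term is still needed to avoid a conservative test.

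**What to change.** 1. In *Study design*, state that participants are allocated from a pre-generated, concealed list in permuted blocks of the six meal orders, 5 participants per order.
2. In *Statistical analysis*, state that iAUC and peak value are compared between meals in a mixed model with meal and visit number (1, 2, 3) as fixed effects and participant as random effect, on log-transformed data if residuals are clearly skewed. This keeps the visit term when the data are not normal, whereas standard paired rank tests have no place for one.
3. Include the visit term whether or not the orders end up balanced, and do not adopt balance without it.

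This model does not cover every listed outcome. Concentrations repeated over the sampling times need a time structure, and time of peak takes only the sampled values, so both need their own specification.

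**Cost.** A different order list and one model factor: 58 to 56 error degrees of freedom with 30 completers, and no added participants, visits or samples. If orders are unbalanced and there is no drift, the visit term costs about 1 to 2 power points. The order list must be fixed before the first meal is given.

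### Post-meal glucose concentrations, and to a lesser extent peak glucose, are primary measures compared without that session's fasting value, which may cost some precision, mainly at late time points

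*Combined protocol and SAP*

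**What the plan says.** Under Glycaemic response (GR), glucose is sampled at -5 and 0 min in each session, with "the baseline value taken as a mean of these two values". Under Insulinaemic response (IR) the same two times are used: "Blood samples in the fasting state will be obtained five minutes apart (-5 and 0 min) for measuring baseline insulin levels". For insulin the plan does not say that the two readings are averaged.

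The only stated use of the baseline is in the incremental area, computed "ignoring the area beneath the baseline".

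Statistical analysis then lists, for comparison between products, the concentrations, the "peak blood glucose/insulin value and time of the blood glucose/insulin peak" and the iAUC. Outcomes puts "blood glucose/insulin concentrations, peak and the time at which peaks occur" alongside iAUC in the primary outcome. The test is left as parametric or non-parametric, depending on a normality check. No increment, change score or covariate is named for peaks or concentrations, and the term incremental is attached only to the area.

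On design: "Participants will act as their own controls", and the meals are taken "in random order on separate days, with a one-week gap between measurements".

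**The concern.** A post-meal glucose value is partly that morning's fasting level and partly the response to the meal. The crossover removes each person's usual fasting level. It does not remove the departure from that level on a given morning, and sessions are a week apart. So far as that departure carries into later values, it adds noise to the meal contrast, even though the study has measured it twice.

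What is at stake is precision. A chance fasting difference between two meals can pass into the difference in concentrations or peaks, and the standard error may be larger than the collected data require. The effect should be greatest at about 120-180 min, where the curve is nearer to fasting and fasting variation can be a larger share of what remains. The sample size of 30 is stated without an SD, effect size or power, so no known margin exists to absorb a loss.

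**Working it through.** **No figure to reproduce.** Participants says only "A sample size of 30 participants will be recruited". For orientation, a paired contrast with n = 30 and two-sided 0.05 (sidedness is not stated) has 80% power at a standardised within-person difference of 0.53.

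**Inputs from the documents.** 30 participants, 3 meals each, 2 fasting readings per session.

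**Assumed inputs (glucose, mmol/l).** The documents give none of these.
- Within-person day-to-day SD of fasting level, sb: 0.2-0.3 (midpoint 0.25).
- SD of a single reading, sr: 0.2.
- Remaining within-person SD, se: 0.6-1.0 for the peak (midpoint 0.8); 0.3-0.5 at 150-180 min (midpoint 0.4).
- Carry-through of a fasting shift into the later value, λ: 0, 0.5 or 1.

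**Variance cut from a covariate** (mean of two readings):

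cut = (λ·sb²)² / [(sb² + sr²/2)·(λ²·sb² + se²)]

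Worked midpoints, with sb² = 0.0625 and sr²/2 = 0.02:
- Peak, λ = 0.5: 0.03125² / [0.0825 × (0.015625 + 0.64)] = 0.000977/0.0541 = 1.8%.
- Late, λ = 0.5: 0.000977 / [0.0825 × (0.015625 + 0.16)] = 0.000977/0.0145 = 6.7%.
- Late, λ = 1: 0.0625² / [0.0825 × (0.0625 + 0.16)] = 0.00391/0.01836 = 21%.

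Ends of the range, λ = 1:
- Peak: 0.0016/(0.06 × 1.04) = 2.6% to 0.0081/(0.11 × 0.45) = 16.4%.
- Late: 0.0016/(0.06 × 0.29) = 9.2% to 0.0081/(0.11 × 0.18) = 40.9%.

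| Carry-through | Peak glucose: range (midpoint) | Late glucose: range (midpoint) |
|---|---|---|
| Full (λ = 1) | 3-16% (7%) | 9-41% (21%) |
| Half (λ = 0.5) | 1-5% (1.8%) | 3-16% (7%) |
| None (λ = 0) | 0% | 0% |

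**Cost of the covariate.** 90 observations - 30 participants - 2 meal terms = 58 error degrees of freedom, so the variance rises by about 1/(58 - 2) = 1.8%. With two period terms it is 1/54 = 1.9%. Net at midpoints with half carry-through: peak 0.982 × 1.018 = 1.00, no gain; late 0.933 × 1.018 = 0.95, a gain of about 5%.

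**Check in terms of correlation.** Let rho be the within-person, between-session correlation of fasting level with the outcome. The variance ratio is (1 - rho²)(1 + 1/54): 1.02 at rho 0, 0.98 at 0.2, 0.86 at 0.4 and 0.65 at 0.6. Break-even is near rho 0.14. Simulation (30 people × 3 sessions, 4000 runs) gave 1.02, 0.98, 0.85 and 0.64. A separate simulation with participant fixed effects kept type I error at 5.0-5.4% after adjustment.

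**Chance fasting imbalance between two meals.** SE = sb·√(2/30) = 0.052 to 0.077 mmol/l.

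**Simple change from baseline.** The variance ratio against unadjusted values is [(1 - λ)²·sb² + se² + sr²/2] / (λ²·sb² + se²). For the peak with half or no carry-through it runs from 1.02 to 1.31, a loss. For example, λ = 0, sb = 0.3, se = 0.6 gives (0.09 + 0.36 + 0.02)/0.36 = 1.31.

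**The case against.** The strongest reply is that, for the peak, the gain may not exist. At mid-range values with half carry-through the 1.8% cut is cancelled by the 1.8% cost, and part of the half-carry-through range is a net loss. This stands, and it is why the point rests mainly on late glucose concentrations.

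A reader might infer that precision is lost for every glucose and insulin measure. The documents do not support that. They give no variances or correlations, and nothing has been quantified for insulin. If fasting insulin is small beside the peak, the gain there is probably negligible. Time of peak is hardly affected, and iAUC already uses the baseline. A reader might also take the most favourable corner as typical: with sb = 0.3, se = 0.3 and one-for-one carry-through, simulated power at a late time point rises from 0.61 to 0.82. At midpoints with half carry-through the same starting power moves only to about 0.63. Nor is there bias: an unadjusted comparison in a randomised crossover is valid.

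Two further replies have force. That the values are compared unadjusted is read from silence: the plan names neither scale nor model. A meal-by-time analysis that included the fasting samples would already reflect change from fasting, and the text does not exclude it. Also, the Protocol section limits session variation through an overnight fast, morning testing and restrictions the day before. Both limit the size of the problem. Neither supplies the missing adjustment.

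**Conclusion.** The point holds as a modest matter of efficiency. On its plain reading, the plan makes no use of a twice-measured fasting value when comparing two kinds of primary measure. Adjustment is worthwhile where fasting level correlates with the later value, within person, above about 0.14. That is plausible for glucose at 120-180 min and uncertain for peak glucose.

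Across half to full carry-through the variance cut, before the cost of about 1.8%, is about 3-41% late and 1-16% for the peak. These ranges depend wholly on the assumed SDs, and the late SDs were set for 150-180 min. The possible loss is small and bounded, while the possible gain is larger, so the change is worth making before data are seen. Choosing the adjustment afterwards would add an analyst's choice.

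**What to change.** In Statistical analysis, state that:

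- Post-meal concentrations and peak values of glucose and insulin will be compared between meals in a linear or mixed model with participant, period and meal.
- The session's fasting value, defined for both glucose and insulin as the mean of the -5 and 0 min readings, will be a covariate. It will be entered as the deviation from the participant's own mean over the three sessions, so that differences between people do not distort the slope.
- The slope will be fitted separately at each time point, or with a fasting-by-time term in a joint model, because carry-through is unlikely to be the same throughout.
- Insulin will be log-transformed if skewed, in place of a switch to a rank test. A standard rank test of three paired meals takes no session-level covariate.

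Do not substitute simple change from baseline, which loses precision when carry-through is partial or absent. Leave the iAUC definition as it is.

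Cost: a short paragraph of analysis text and a model in place of simple paired or rank tests, with about 1.8% loss of precision per outcome if fasting level proves unrelated to later values. No new samples, visits or participants are needed.

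### The primary outcome is 14 or more glucose and insulin measures, each tested at P<0.05, with no deciding measure, window or contrast, no success rule and no multiplicity control

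*Combined protocol and SAP*

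**What the plan says.** The Outcomes section states that the "primary outcome will be the GR and IR, as measured by the incremental area under the curve, blood glucose/insulin concentrations, peak", and then adds the times at which peaks occur. Glucose and insulin stand on an equal footing.

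The Statistical analysis section lists what will be compared in Phase I: concentrations, peak value and time of peak, and "glucose/insulin iAUC (at 60, 90, 120 and 180 min"). On method it says "Parametric or non-parametric tests will be used as appropriate to compare the following between the products", the choice to follow a normality check. On error control it says only "Statistical significance will be set at" P<0.05.

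The Study design section describes "three meals: one reference meal (50 g available carbohydrate) and two test meals". The Glycaemic response section fixes eight post-meal samples: "Further blood samples will be taken at 15, 30, 45, 60, 90, 120, 150 and 180 min after starting to drink". The Insulinaemic response section gives the same eight times.

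No section ranks the measures, the windows, the two analytes or the meal contrasts. None says what would count as a positive primary result, and none mentions adjustment for multiple tests.

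**The concern.** A threshold of 0.05 limits the false-positive chance of one test. It does not limit it for a primary outcome made up of many tests when a significant result on any of them may be reported as the primary finding. The plan does not tell the investigators to report that way, but nothing in it prevents them.

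The list of measures is fixed in advance, but the choice within it is not. After the data are seen, emphasis could fall on glucose or insulin, on iAUC to 60 or to 180 min, on peak or time of peak, or on either protein dose, and the report would still follow the protocol. Calling the reference meal the reference suggests that each protein meal is to be compared with it. However, the analysis text does not fix that contrast or exclude dose 1 versus dose 2. What is at stake is whether a primary claim from this trial carries the error rate that a reader would take from P<0.05.

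**Working it through.** **1. The plan's own figure.** The only error rate stated is 0.05 per test. In the 60-scenario simulation below, a single three-meal test rejected in 4.5–5.6% of null trials, so the per-test rate is reproduced. The sample size of 30 comes with no power, effect size or SD, so there is nothing to reproduce there.

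**2. Count of primary measures.** Each of the two analytes has four iAUC windows, one peak and one time of peak, plus concentrations.
- One concentration test per analyte: 2 × (4 + 1 + 1 + 1) = 14.
- Each of the eight post-meal times tested: 2 × (4 + 1 + 1 + 8) = 28.

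**3. Reference value if the tests were independent.** 1 − 0.95^14 = 0.51 and 1 − 0.95^28 = 0.76. These are not estimates, because the nested windows and the other measures of one curve are correlated.

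**4. Simulation with correlation.**

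*From the documents:* 30 participants, three meals, the sampling times, and iAUC by the trapezoid rule ignoring area below baseline.

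*Assumed:* no meal effect; all 30 complete; any one P<0.05 counts as positive. In the 60-scenario set:
- visit amplitude SD (log scale) 0.15 or 0.30
- serial correlation time constant 20, 60, 120, 240 or 480 min
- visit noise 10% or 35% of mean amplitude
- glucose–insulin correlation 0, 0.4 or 0.8
- 8,000 trials per scenario (Monte Carlo SE at most about 0.6 points)

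The other sets varied the curve shapes and correlations, to see how far the answer depends on them.

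Chance of at least one P<0.05 when protein has no effect:

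| Basis | 14 measures | 28 measures |
|---|---|---|
| Repeated-measures F test per measure, 60 scenarios (min–median–max) | 19.0–22.9–30.4% | 26.8–38.1–59.0% |
| Same test, separate set of 36 scenarios | 22–32% | 33–60% |
| Same test, separately programmed, 24 scenarios | 20.7–31.0% | 32.5–62.0% |
| Same test, further set of 18 scenarios | 18–28% | 28–49% |
| Same test, block correlation (0.7–0.9 within analyte, 0–0.7 between) | 18–35% | 21–47% |
| Same test, uniform correlation 0.9 | 13.6% | 17.5% |
| Same test, uniform correlation 0.95 | 11.2% | 13.2% |
| Each protein meal versus reference, paired t, unadjusted, 60 scenarios (min–median–max) | 32.0–37.7–47.8% | 43.3–57.9–81.1% |
| All three pairwise contrasts, paired t, unadjusted, 24 scenarios | 43–61% | 60–91% |

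The headline ranges, 19–32% and 27–60%, are the union of the first two rows. The three-meal F test is the lenient case; unadjusted pairwise contrasts give higher rates.

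**5. A small designated set.** Example: glucose iAUC and insulin iAUC to 180 min, each protein meal versus reference, so 2 × 2 = 4 tests. Adding dose 1 versus dose 2 makes 2 × 3 = 6. Over the 60 scenarios:
- Four tests: 13.4–17.7% unadjusted, 3.2–5.0% with Holm.
- Six tests: 17.7–23.7% unadjusted, 2.9–4.8% with Holm.

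**6. Power cost.** Paired t test, n = 30, 29 degrees of freedom, assumed standardised paired difference 0.529 (not in the documents), so the noncentrality is 0.529 × √30 ≈ 2.90. Power is 80% at 0.05, 60% at 0.05/4 = 0.0125, and 53% at 0.05/6 = 0.0083.

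**The case against.** The strongest objection is that the error rates rest on a rule the protocol does not contain. It opens with "The aims of this study are to examine"; it states no hypothesis and claims no overall 5% error rate. Read as a descriptive physiological crossover with a fixed list of measures, all reported, the multiplicity would be visible to any reader. This stands as a condition on the figures, which apply only if any one significant result counts. It does not remove the gap: the plan separates primary from secondary outcomes and sets a significance threshold, and that separation does little when at least 14 results share the primary label.

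A second objection is that the percentages depend on unknown correlations. That is correct. A uniform correlation of 0.9 falls below the headline ranges, and one set of curves reaches 62% for 28 tests. The highest value in the 60-scenario set needs a 20-minute time constant, under which the serial component of samples 30 minutes apart correlates only exp(−30/20) = 0.22, together with no glucose–insulin correlation. The 28-test count is also only one reading of concentrations; a single repeated-measures analysis per analyte would fit the text equally well.

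Third, the simulations used repeated-measures ANOVA or paired t tests throughout, not the planned choice after a normality check, and this includes time of peak, which can take only sampled values. That limitation stands but is unlikely to reverse the result.

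Finally, the unspecified Phase II trigger, "Depending on the outcome of Phase I, samples will be subsequently analysed to determine the concentrations of GLP-1 and GIP", is a separate and minor matter. The blood is already stored, and this point carries no weight here.

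**Conclusion.** The concern holds. It is a matter of text that the primary outcome comprises 14 measures, or 28 on the per-time-point reading, and that the plan designates none of them, gives no success rule and controls no familywise error.

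The size of the consequence depends on assumptions: no protein effect, 30 completers, any one P<0.05 counted as positive, and correlations that the documents do not supply. On those terms the false-positive chance is about 19–32% with 14 three-meal tests and 27–60% with 28. These are not bounds. The lowest value in any scenario tried was 11%, still more than twice the nominal 5%. Because the defect lies in the definition of the primary outcome, it touches any primary claim, and analysis after the data are seen cannot fully repair it. It should be settled before then.

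**What to change.** Amend the Outcomes and Statistical analysis sections before data are seen:

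1. Designate a small primary set by measure, window and meal contrast. One example is the four-test set in step 5 above. The documents do not rank the options, so the sponsor may choose others.
2. Say whether dose 1 versus dose 2 is primary or secondary.
3. State what counts as a positive primary result.
4. Hold familywise error at two-sided 0.05 across the primary set, by Holm or by an order of testing fixed in advance.
5. Make the remaining windows, peak, time of peak and concentrations secondary, reported as estimates with 95% confidence intervals.

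The change is to text alone, with no extra visits, samples or participants, but the sponsor must make design decisions. Measures moved to secondary can no longer be claimed as primary findings. The power loss in step 6 is for Holm's strictest step, so it is the worst case under Holm. A fixed order leaves the first test at its full 80%.
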